**3. List any restrictions on use of other drugs or treatments.**

1. Medications being taken to lower blood glucose, such as Pramlintide, Metformin, GLP-1 Analogs such as Liraglutide, and nutraceuticals intended to lower blood glucose
2. Any other medication that the investigator believes is a contraindication to the subject's participation

**Statistical Considerations**

**1. Is stratification/randomization involved? Yes**

**► IF YES, describe the stratification/ randomization scheme.**

1. Randomization will be done at the Screening Visit and will be performed by simple randomization schedule (like flipping a coin)
2. Randomization will not be blinded; it will determine the order of the Experimental and Control Admissions after the initial 14-28 days of Data Collection

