**2. What is the study design?**

This is a single-center randomized crossover trial. We will target completion of 15 adults (age 18-65 years) with Type 1 Diabetes who use an insulin pump. Subjects will undergo an initial Screening Visit and randomization will occur if the visit is successfully completed. After completion of the Screening Visit, each subject will participate in an at home Data Collection Period that will last approximately 14 to 28 days while using their personal insulin pump, a personal glucometer, a study CGM, and a study activity tracker (i.e., Fitbit). This data collection period may be extended to gather more days of quality data, if needed per principal investigator judgement. Once the data has been collected and processed, subjects will participate in two 24-hour admissions (Experimental and Control Admission) in a semi-controlled environment (i.e., hotel), performed in the assigned random order. During both admissions, subjects will use their personal insulin pump and glucometer, and a study CGM. Subjects will be admitted around 9AM. Subjects will be advised to have their home breakfast per their normal routine; around 12PM, they will be provided lunch, followed by an exercise session around 2:30PM. The exercise session will consist of three 15-minute bouts of moderate-intensity exercise (i.e., stationary bicycle). Around 7PM, subjects will be provided a controlled dinner; the SI-informed bolus calculator will be used in the Experimental Admission while standard therapy will be used in the Control Admission. Subjects will then be observed overnight and discharged in the following morning.

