**3. How many subjects will be enrolled at all sites?**

This is a single site clinical trial to be completed at UVa. Given the potential of a 40% dropouts/withdrawals rate, up to 25 people will be enrolled.

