**Power/Precision of the study to address major study endpoints:**

As a safety and feasibility study, this trial is not powered to a specific outcome. A sample size of 15 subjects has been chosen with the purpose of being able to compute the Cohen's  $d$  once the trial is completed. Cohen's  $d$  is defined as the difference between two means divided by a standard deviation for the data (standardized difference between two means), and will serve as effect size to appropriately power the subsequent main trial.

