**4. What is your plan for primary variable analysis?**

We will compute CGM metrics with the primary outcome analysis of LBGI by CGM following dinner, comparing the Experimental Admission to Control Admission.

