#### **Study Procedures-Biomedical Research**

**1. What will be done in this protocol?**

##### ***Visit 1: Screening Visit.***

All subjects will be consented and receive a history and physical. Study eligibility will be reviewed. If a subject satisfies all the study inclusion criteria and does not meet any exclusion criteria, he/she will be enrolled in the study and randomized to the Experimental or Control Admission occurring first.

At the Screening Visit, the following procedures will be performed, and criteria will be checked and documented:

1. Signed and dated informed consent
2. Inclusion and exclusion criteria
3. Demographics (date of birth, gender, race and ethnicity)
4. Medical history
5. Details of the diabetic history: duration of disease (number of years), diagnosis details, current treatment (including basal rates or basal insulin dose(s), carbohydrate ratios, insulin sensitivity factors, target glucose, average total daily insulin, history of DKA, history of severe hypoglycemia, and self-monitoring blood glucose values)
6. Surgical history
7. Menstrual history (females) and sexual activity/contraception (females)
8. Allergies
9. Medications and supplements
10. Social history including drinking and smoking
11. Physical examination
12. Electrocardiogram (ECG)
13. Weight and height
14. Vital signs
15. Blood and urine testing for screening labs:
  - Hemoglobin A1c
  - Comprehensive chemistry panel
  - TSH
  - Pregnancy test: either urine or qualitative serum HCG in women with childbearing potential. If not performed, document reason (surgically sterile, postmenopausal)

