If a study subject has had a recent physical exam (less than 6 months) and blood work done (less than one month), the study physician will have the discretion to repeat any test as needed. Once all results of the screening evaluations are available, a decision will be made to determine the subject's eligibility for the study or if one or more parts of the screening will have to be repeated. If at the first screening or repeated screening an exclusionary condition is identified, the study subject will be excluded from participation and referred to their primary care physician as needed. If the study subject is pregnant, the study physician will discuss the results of the urine/blood test with the subject, and the subject will be asked to seek confirmation of the test and the appropriate medical care. The screening visit will last approximately 2 hours. If the subject cannot schedule Visit 2 within 16 weeks of screening, screening labs, vital signs, and recent medical illness/medications will be re-evaluated. The study physician will have the discretion to repeat any test as needed. If a subject meets all the study criteria, he/she will be enrolled in the trial and randomized to begin the experimental or control admit first. Visit 2 may be completed at the conclusion of Visit 1 if all eligibility requirements are met.

All subjects will be advised to contact the study team in the event of a febrile illness within 48 hours of the study visits, so that the study visits can be rescheduled. All subjects will be given

instructions to bring all of their current medications and insulin pump supplies with them for use during or after the study visits.

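### Coin-flip order with no named period term lets chance imbalance pass part of any period effect into the mean LBGI difference; blocking plus a period term is a cheap, minor improvement

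*Combined protocol and SAP*

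**What the plan says.** - **Allocation.** Statistical Considerations, question 1: "Randomization will be done at the Screening Visit and will be performed by simple randomization schedule (like flipping a coin"). No blocking or other balance rule is given.
- **Timing.** Study Design, question 2, agrees: "Subjects will undergo an initial Screening Visit and randomization will occur if the visit is successfully completed". The Visit 1 section says it twice: "he/she will be enrolled in the study and randomized to the Experimental or Control Admission occurring first" and "he/she will be enrolled in the trial and randomized to begin the experimental or control admit first".
- **Analysis.** Statistical Considerations, question 4, plans a "primary outcome analysis of LBGI by CGM following dinner, comparing the Experimental Admission to Control Admission". No test, model, period term or sequence term is named there or elsewhere in the statistical section.
- **Use of the result.** The Power/Precision paragraph defines Cohen's d as a difference in means "divided by a standard deviation for the data" and says that it "will serve as effect size to appropriately power the subsequent main trial".
- **Numbers.** The target is 15 completers. "Given the potential of a 40% dropouts/withdrawals rate, up to 25 people will be enrolled". The stopping criteria allow a non-completer to be replaced, with no rule for restoring balance between the two orders.
- **Spacing.** The admissions are at least 48 hours and at most 100 days apart.

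**The concern.** In a two-period crossover, each subject's Experimental-minus-Control difference contains the treatment effect plus or minus the period effect, with the sign set by the order. With equal numbers in the two orders, the period effect cancels from the overall mean. With unequal numbers it does not, unless the analysis allows for it. A coin flip with 15 completers often gives unequal numbers, and the analysis sentence offers no protection.

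At stake is the primary estimate, the mean LBGI difference, and its standard error. An unmodelled period effect also widens the spread of the paired differences. Cohen's d is built from the same data, so it is touched too, but in a less simple way (see the working).

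**Working it through.** **Inputs from the protocol.** 15 completers, 40% loss, up to 25 enrolled, order assigned with probability 0.5 per subject. No period effect, LBGI standard deviation or target effect size is given. Period effects p (second admission minus first) below are therefore assumptions, in SDs of the paired difference with the period effect removed. Loss is taken to be unrelated to order.

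**The plan's own figure.** 15 / (1 − 0.40) = 25, which matches the enrolment ceiling.

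**Chance of an unequal split.** With K ~ Binomial(15, 0.5):
- 10:5 or worse: 2 × P(K ≥ 10) = 2 × 4,944 / 32,768 = 0.302
- 11:4 or worse: 2 × P(K ≥ 11) = 2 × 1,941 / 32,768 = 0.118

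**Share of the period effect in the unadjusted mean.** The mean difference estimates treatment + p × (n control-first − n experimental-first) / 15. The share is 1/15 = 7% at 8:7, 5/15 = 33% at 10:5 and 7/15 = 47% at 11:4. Averaged over coin flips, the absolute share is 21% and the signed share is zero.

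**Size at 10:5.** For p = 0.1, 0.1 × 1/3 = 0.03 SD. For p = 0.25, 0.25 × 1/3 = 0.08 SD. The sampling standard error is 1/√15 = 0.26 SD.

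**With a period term** (the average of the two sequence means), the shift is zero at any split with subjects in both orders. The variance relative to the unadjusted mean is 15 × 0.25 × (1/n1 + 1/n2):

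| Split | Relative variance |
|---|---|
| 8:7 | 1.0045 |
| 9:6 | 1.042 |
| 10:5 | 1.125 |
| Average over coin flips | 1.086 |

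**Mean squared error of the mean difference (× 15).** Coin flip, unadjusted: 1 + p². Setting this equal to each alternative gives the break-even period effect:
- Coin flip kept, period term added: √0.086 = 0.29 SD
- 8:7 with period term: √0.0045 = 0.07 SD

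In subject equivalents, 8:7 with a period term is worth 15 × (1 + p²) / 1.0045. That is 15.9 at p = 0.25 and 14.9 at p = 0.

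**Cohen's d.** Simulation with the SD of paired differences as denominator, 15 completers and an assumed true d of 0.5. Root mean squared error of d (third decimal subject to simulation error):

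| Period effect | Coin flip, unadjusted | 8:7 with period term |
|---|---|---|
| 0 | 0.300 | 0.305 |
| 0.25 SD | 0.298 | 0.305 |
| 0.5 SD | 0.296 | 0.305 |

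Overall accuracy of d does not improve. Sample d runs high at this size (average 0.53 for a true 0.5 with no period effect), and the SD inflated by an unmodelled period effect happens to pull it down. That is no merit of the coin flip, but it rules out claiming a gain.

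**Blocking and dropout.** With mixed blocks of 2 and 4 and random loss after assignment, the simulated chance of 10:5 or worse is 0 with none lost, 0.8% with 3 of 18 lost, 4.1% with 5 of 20 and 11.1% with 10 of 25.

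**The case against.** The case against acting is substantial, and most of it stands as a limit on how much to claim.

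- **The period effect is hypothetical.** Insulin parameters are to stay fixed, carbohydrate amounts and exercise are matched, and activity and alcohol are to be avoided for 48 hours beforehand. The 100-day maximum gap permits individual drift, but a period term removes only a shift common to all subjects. This stands: the documents neither show a period effect nor exclude one.
- **The unadjusted mean is inferred.** The analysis sentence names no model at all. This also stands, and it is a reason to write the model down.
- **Simple randomization is valid for a pilot.** True. A reader might infer that the primary comparison is biased or the trial compromised. The documents do not support that: over repeated randomizations the unadjusted difference is unbiased, and at the assumed sizes the shift is well below sampling error.
- **The planned use of d raises the stakes.** Because d is meant to power the main trial, a reader might infer that the change would make that sample size more accurate. The simulation shows otherwise. A period term does remove the shift at a given unequal split and the inflation of the SD, but averaged over splits the error in d is no smaller.
- **Blocking at Screening is undone by dropout.** Only in part. The 11% figure assumes that all 25 who consent are randomized and 10 are then lost, but screen failures come out of the 25 before randomization. The under-1% figure rests on an assumed 3 of 18 lost, which is not in the protocol. Late assignment is therefore a refinement, not a necessity.

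**Conclusion.** The point holds as a minor, low-cost improvement to the primary mean difference and its standard error. Certain from the text: order is set by coin flip, and no period term is named. Certain from arithmetic, if loss is unrelated to order: a 30% chance of 10:5 or worse, and one third of any period effect carried into an unadjusted mean at 10:5. Assumed: the size of any period effect. At 0.1 to 0.25 SD the shift at 10:5 is about an eighth to a third of the standard error (0.03/0.26 to 0.08/0.26).

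The gain for the mean difference is about 0.9 of a subject at 0.25 SD, and the loss is about 0.1 of a subject if there is no period effect. Both figures are for an 8:7 split; the gain shrinks as dropout moves completers away from it (break-even at 9:6 is √0.042 = 0.20 SD). The point supports no claim of invalidity and no claim of a more accurate d. Which SD forms the denominator of d is left open by the protocol and is a separate question.

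**What to change.** 1. In Statistical Considerations, question 1, replace the coin flip with small permuted blocks, for example mixed sizes 2 and 4.
2. In question 4, state that the Experimental-minus-Control LBGI difference will be estimated with a period term, as the average of the two sequence means, and that completers will be reported by sequence.

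Adopt both together. A period term with the coin flip kept pays off only above about 0.29 SD, because it costs 12.5% in variance at a 10:5 split.

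Optional: assign order just before Visit 3, once the Data Collection Period is accepted, so that earlier losses do not disturb balance. If this is done, Study Design question 2, Statistical Considerations question 1 and both randomization statements under Visit 1 must be edited to match.

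**Cost.** A new list and one analysis sentence; at 8:7, 0.4% in variance and one degree of freedom. Small blocks in an open-label trial are partly predictable, which matters less here because every subject is due to receive both conditions.

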***Visit 2: Study Equipment Placement & Training and Data Collection Period.***

Visit 1 and 2 can be completed on the same day. All subjects will receive training on the use of the 1) CGM and 2) study-supplied commercially available activity monitor (e.g., Fitbit or similar device). New sensors will be issued to each subject; the CGM may be reused after it has been cleaned as required using a dilute mixture of bleach or another appropriate cleaning agent.

[figure not shown]

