**Data Collection Period**

1. Subjects will collect data for approximately 14 to 28 days prior to Visit 3 and Visit 4.

2. The CGM and insulin pump data will be analyzed by the study team at the end of the Data Collection Period, to determine the SI profile that will be used during the Experimental Admission (Visit 3 or 4). Special emphasis will be noted to the study subject that all meal information (i.e., carbohydrate quantity and insulin) must be recorded in their insulin pump.
3. Subjects will be instructed on how to download the equipment (i.e., personal insulin pump, personal glucometer, study CGM, study activity monitor). Subjects will be asked to provide downloaded data periodically during the data collection period (approximately one time per week) using a web-based diabetes management system (e.g., Diasend, CareLink Pro, etc. – Figure 2) and local diabetes device management software (e.g., Dexcom Studio). The study team will review subject data to ensure proper data collection. Study team will review quantity and quality of the data. Additional download requests may occur depending upon the quality of the data collected.
4. Subjects will be asked to wear the study activity monitor during the data collection phase, removing prior to bathing and participating in water activities. Subjects will also wear the activity monitor to collect information on activity, exercise, heart rate, and sleep. A study Gmail account will be established for each subject. The commercially available app associated with the activity monitor will be placed on the subject's smartphone or subject's personal laptop to facilitate weekly downloading of data. If the subject has an existing personal account with the commercially available activity monitor and the subject would prefer to use their existing personal account rather than creating an anonymous account, the subject will be allowed to do so and the study team would request access to that account.
5. Subjects will be advised to consistently use the bolus calculator (or "wizard") of their insulin pump, and not to use temporary basal rates to compensate for meals.
6. Subject may be asked to repeat up to 4 weeks of the Data Collection Period.
7. If the subject is unable to provide the downloaded data from home, the subject will be asked to return to the office so the study team can assist them.
8. The subject may return to the office at any time for additional support.

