**Figure 2: Example of web-based diabetes management systems used for data upload (Diasend top, CareLink bottom)**

### **Visit 3 and 4: Research Admission (i.e., Hotel).**

The Experimental and Control Admission will be separated by at least 48 hours with a maximum of 100 days. The order of these two visits will be randomly selected. Subjects will be admitted to the research location at approximately 9:00AM and will be discharged after approximately 24 hours.

All procedures will be the same for Visit 3 and Visit 4 with the following exception:

- Insulin Boluses during the Control Admission: All meal and correction boluses during the control admission will be per the subject's usual insulin parameters. The two admissions will use consistent insulin-to-carbohydrate ratio, correction factor, and basal profiles.
- Insulin Boluses during Experimental Admission: The dinner meal bolus will be determined with the use of the SI-informed bolus calculator during the Experimental Admission. The calculations will be performed on a study smartphone (Diabetes Assistant, DiAs), approved by the study MD, and subsequently communicated to the subject. The suggested insulin bolus will be administered through the subject's personal insulin pump. The study physician will override the insulin dose computed with the use of the SI-informed bolus calculator at any time if he/she considers it is not safe for the participant subject in the following way:

- 1 The dinner insulin dose suggested by the SI bolus calculator will be  $\pm 30\%$  of the dose that the subject should receive while using his/her own insulin pump bolus calculator (usual care). This is by design of the SI bolus calculator.
- 2 If the licensed endocrinologist conducting the study considers the dinner dose suggested by the SI bolus calculator to be unsafe he/she will override this dose.
- 3 In order to avoid bias between the physicians involved, every effort will be made to have the primary MD supervising all the experimental admission.

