#### **Glycemic Guidelines during Research Visit**

1. Upon arrival, the subject will be asked to check the CGM reading and ketone concentration using the study ketone meter. If CGM <70 mg/dL or >300 mg/dL or ketone test is >0.6 mmol/L, study physician will suggest appropriate treatment. The study subject may continue participation in the trial once CGM is between 70-300 mg/dL and ketone concentration ≤0.6 mmol/L.
2. If CGM >300 mg/dL for more than 1 hour or >400 mg/dL at any time, study physician will be notified to suggest appropriate treatment and ketones will be checked. If ketone

concentration is  $>0.6$  mmol/L, the study team will check the insulin pump infusion site and correction insulin will be administered per study physician judgement via the subject's insulin pump or study-supplied insulin pens. The study team will monitor CGM decay and ketones will be checked every 60 minutes until  $\leq 0.6$  mmol/L.

3. If ketone concentration is  $\geq 3.0$  mmol/L, the study subject will be discontinued, DiAs will be changed to Stopped mode, and appropriate medical treatment will be sought. If the subject is discontinued, he/she may repeat the admission at discretion of the PI.
4. If CGM  $<60$  mg/dL at any time, subjects will be given approximately 16 grams of fast-acting rescue carbohydrates. Study team will monitor CGM rise and will consider treating again if CGM  $<80$  mg/dL after 20 minutes. Hypoglycemic treatments can occur at any time per study physician request.
5. If CGM  $<80$  mg/dL at any time during the exercise session, subjects will suspend the exercise activity and take approximately 8-16 grams of fast-acting rescue carbohydrates. Study team will monitor CGM rise and will consider treating again if CGM  $<80$  mg/dL after 20 minutes. Exercise activity will resume once CGM  $\geq 80$  mg/dL.
6. Prior to the subject being discharged from the admission after either completing the study procedures or discontinuation, the CGM and ketones will be checked. The subject will be discharged once the CGM reading is between 80-250 mg/dL and ketone concentration  $\leq 0.6$  mmol/L.

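### The admission order is randomized at screening, unblinded and with no stated release point, although the arms differ only from the dinner bolus at about 7PM; later release would protect the pre-dinner phase of Visit 3

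*Combined protocol and SAP*

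**What the plan says.** **Timing and openness.** Statistical Considerations, item 1: "Randomization will be done at the Screening Visit and will be performed by simple randomization schedule (like flipping a coin"; then "Randomization will not be blinded; it will determine the order of the Experimental and Control Admissions after the initial 14-28 days of Data Collection". The Visit 1 section agrees: once the criteria are met, "he/she will be enrolled in the study and randomized to the Experimental or Control Admission occurring first". No section says that the order is concealed, who learns it, or when.

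**What follows randomization.** On equipment placement and training: "Visit 1 and 2 can be completed on the same day". On data collection: "Subjects will collect data for approximately 14 to 28 days prior to Visit 3 and Visit 4". That period may be repeated for up to four weeks, and Visit 3 may fall up to 100 days after it ends (Data Collection Period, items 6 and 10).

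**How the arms differ.** Visit 3 and 4: Research Admission: "All procedures will be the same for Visit 3 and Visit 4 with the following exception". The exception concerns boluses, and the only experimental element is the dinner bolus. Check-in is at about 9AM and dinner at about 7PM.

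**Pre-dinner care.** Insulin parameters and the carbohydrate amounts designated by the subject are to be consistent across admissions, and the glycemic guidelines set CGM triggers. The same guidelines also leave room for judgement, for example in item 4: "Hypoglycemic treatments can occur at any time per study physician request".

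**Existing safeguards.** The text on physician bias deals only with approval and override of the dinner dose.

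**The concern.** Nothing done to the subject before dinner depends on the arm, so nobody treating the subject needs to know it until the dinner bolus is calculated. Under the plan as written, staff and subject may know it all day.

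If pre-dinner treatment were handled differently on Experimental days, subjects could reach dinner with different glucose or insulin on board for reasons unrelated to the calculator. Post-dinner LBGI is the primary outcome (item 4, primary variable analysis). LBGI is also to be compared overall (Study Objectives and Endpoint Definitions), and pre-dinner treatment would enter that measure directly. The resulting Cohen's *d* is meant to power the main trial, so a distortion would carry forward.

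**Working it through.** **1. Enrolment figure.** The plan's one reproducible sample-size figure is not in dispute: 15 completers at 40% loss gives 15 / (1 − 0.40) = 25, as stated. No alpha, power, effect size or SD is given.

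**2. Gap from randomization to Visit 3.** Inputs: Visit 2 possible on the day of Visit 1; data collection 14 to 28 days; repeat up to 28 days; Visit 3 within 100 days of its end.
- Shortest: 0 + 14 = about 14 days.
- One full collection period: 28 + 100 = 128 days.
- With the four-week repeat: 28 + 28 + 100 = 156 days.
- With Visit 2 also at week 16: 112 + 28 + 28 + 100 = 268 days. Week 16 only triggers re-evaluation of screening, so this is an example and not a limit.

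**3. Window in which the arm is irrelevant to care.** 9AM to 7PM is 10 hours, and 10 / 24 = 42% of an admission.

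**4. What is fixed and what is left to judgement before dinner.**

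| Item | Status | Where |
|---|---|---|
| Insulin-to-carbohydrate ratio, correction factor, basal profile | Same in both admissions | Visit 3 and 4: Research Admission |
| Designated lunch and dinner carbohydrates | Matched across admissions | Procedures during Research Visit, items 2 and 5 |
| Meal and correction boluses | Based on CGM | Same, item 9 |
| Pausing and resuming exercise | CGM rule at 80 mg/dL | Glycemic Guidelines, item 5 |
| Rescue carbohydrate | CGM triggers at 60 mg/dL, and at 80 mg/dL during exercise | Items 4 and 5 |
| Additional hypoglycemia treatment | Physician request | Item 4 |
| Carbohydrate amount during exercise | Range of 8 to 16 g | Item 5 |
| Whether to treat again after 20 minutes | Staff consider it | Items 4 and 5 |
| Correction insulin at high CGM with raised ketones | Physician judgement | Item 2 |

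The last four rows are where knowledge of the arm could act.

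**5. Route to the outcome.** Carbohydrate shifts glucose, and correction insulin shifts insulin on board. Both quantities enter the bolus formula in the Background section, so the dose would respond to part of any difference at 7PM. The net effect on LBGI cannot be computed, because no LBGI SD and no rescue-treatment rate are given.

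**6. Reach of later release.** Pre-dinner hours with the arm known, among completers:
- now: 15 × 2 × 10 = 300;
- with release at the Visit 3 dinner bolus: 15 × 1 × 10 = 150.

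The figure does not reach zero, because in a two-period crossover the second arm follows from the first.

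**The case against.** **Disclosure at screening.** A reader might infer that everyone is told the order at screening. The documents say only that randomization is not blinded; they do not say who is told or when. What stands is that no release point is stated.

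**Bias during data collection.** A reader might infer that knowing the order for months biases the SI profile or the choice of parameters. The documents do not support this. Every completer receives both arms, one parameter set serves both admissions, and the profile is used only in the Experimental Admission, whichever comes first. The long gap does not itself create a difference between arms.

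**Eligibility.** Randomizing at the visit might seem to precede the laboratory results. But the plan says "Once all results of the screening evaluations are available, a decision will be made to determine the subject's eligibility", and subjects are randomized only if they meet the criteria. At most the wording on timing is loose.

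**Ten hours of free discretion.** The table shows otherwise. Parameters and designated carbohydrates are matched, exercise pauses follow a rule, and much of the day is quiet activity.

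**A bias as large as the treatment effect.** With an assumed 60 g dinner and 10 g/U, one might set 16 g / 10 = 1.6 U against the largest modulation, 0.30 × 60 / 10 = 1.8 U. Neither assumption is in the documents. The stated exercise range differs by only 8 g, or 0.8 U on the same ratio. Exercise starts at about 2:30PM, so carbohydrate given then is partly absorbed by 7PM. The formula also adjusts for current glucose and insulin on board. The comparison does not measure bias.

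**A reason to know the arm early.** The plan wants the primary physician at Experimental Admissions. That reason is weak, because elsewhere it seeks the primary physician at all admissions (Procedures during Research Visit, item 5).

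**A partial remedy in a small pilot.** This is fair. Visit 4 stays open, post-dinner treatment inside the primary window stays open, and the trial is not powered for any outcome.

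**Conclusion.** The point holds as a cheap improvement and not as a demonstrated bias. The order is fixed and unblinded from screening, with no release point, while the admissions are procedurally the same until the dinner bolus. Some pre-dinner treatment that can influence the primary outcome is left to people who may know the arm. Whether they would act differently, in which direction and by how much, cannot be settled from the documents.

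The gain from later release is bounded: the pre-dinner phase of Visit 3, which is 15 of 30 completer admissions or 150 of 300 pre-dinner hours. This assumes 15 completers, one admission per arm, and an order that is otherwise known throughout both days. A Visit 3 that had to be repeated after release would also run with the order known.

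There is a second benefit. The plan expects to lose about 25 − 15 = 10 of 25 enrolled. Subjects lost before Visit 3, a number the documents do not give, would no longer be part of the randomized set.

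**What to change.** 1. Move randomization from the Screening Visit to Visit 3, after eligibility is confirmed and the SI profile and admission parameters are locked. Amend Study Design item 2, Statistical Considerations item 1 and the Visit 1 text together so that they agree.
2. Have someone who is not running the admission hold the order. Release it by sealed envelope or DiAs code only when the Visit 3 dinner bolus is to be calculated. Visit 4 takes the other arm.
3. Have the SI profile ready for every Visit 3, so that either arm can be delivered. The profile is built at the end of data collection anyway, and DiAs is connected at both visits.
4. Record all pre-dinner hypoglycemia treatments and correction insulin with time and amount, and tabulate them by arm, separately for Visit 3 and Visit 4. The concealed Visit 3 comparison then gives a reference for the open one.

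The cost is amendment wording, envelopes or a release code, slightly more preparation before Visit 3, and physician cover planned without knowing the arm. Sample size, the glycemic guidelines, and physician approval and override of the dose are unchanged. The Visit 4 arm and post-dinner care remain open, and the report should say so.
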